Subjects are presented with study drug (OXE-103) treatment. If they decline, they will be offered participation in non-treatment control Arm. If subjects choose treatment and fail screening, they may be offered non-treatment control Arm option.

PART A ARM 1 = OXE-103 treatment

PART A ARM 2 = Non-treatment concurrent control

[figure not shown]

PART B: ACUTE DAY 1

Subjects choosing to participate in study are randomized to receive study drug (OXE-103) or placebo.

PART B ARM 1 = OXE-103

PART B ARM 2 = Placebo

Regulatory:

Oxeia's license through Daiichi Sankyo includes cross-reference to an open IND at the FDA. In November 2017 Oxeia submitted a pre-IND briefing package for a proposed Phase 2 study. The FDA response supported moving into Phase 2. This study will be conducted under an investigator sponsored IND cross referencing the existing open FDA IND.

Manufacturing, Partnerships, Current GMP Drug Supply:

The company maintains access to clinical grade drug supply manufactured by Daiichi Sankyo, Ltd. for subcutaneous injection. Multiple lots have been produced and are available for clinical study use. The drug product is manufactured in compliance with good manufacturing practice. It is supplied in a 5 mL clear, borosilicate glass vial with a butyl-rubber closure (fluoro-resin film laminated), as a sterile lyophilized white powder or cake equivalent to 14 mg of OXE-103 as the active ingredient and sucrose (inactive ingredient). Matching placebo and diluent product is also available.

OXE-103 drug product, placebo, and diluent should be stored refrigerated between 2°C to 8°C (35.6°F to 46.4°F). Reconstituted OXE-103 for SC administration 14 mg (in 5 mL multi-use vials) is stable for up to 14 days at 10°C or for up to 3 days when stored at 25°C/1000 Lux. The reconstituted drug product (and placebo) should be stored refrigerated at 2°C to 8°C (35.6°F to 46.4°F).

Upon request from the study team, Oxeia Biopharmaceuticals will coordinate shipment of all necessary study drug product, placebo, and diluent to the study team. Shipments will include all appropriate certificates of quality, as may be necessary for any FDA-related audits and submissions.

Proposed Clinical Trial

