We propose a pilot study to treat 1) Sub-acute concussion with OXE-103 in Part A and 2) Acute concussion management with OXE-103 within 24 hours of presentation to the Trauma Unit in Part B. For Part A, we will recruit subjects from the University of Kansas Health System Center for Concussion Management (CCM) clinics which include Neurology, Sports Medicine, and Neurosurgery/PM&R. For Part B, we will recruit subjects from the University of Kansas Health System Trauma Unit. In Part A we will compare an open-label treatment arm (OXE-103) to a non-treatment concurrent control arm. Part B will be randomized double blind 1:1 to treatment with OXE-103 and placebo. We will compare these using self-report symptom scoring, quality of life questionnaires, computerized cognitive testing assessing executive function, memory and processing speed, and accelerometer-based balance scoring. The exploratory nature of this study is not powered to yield statistically significant outcomes, but will allow detection of trends within subjects and between groups, will support comparison with standard tests of neurocognitive functions, and will provide sample size estimates for future studies of people with persistent concussion related symptoms.

This study is highly relevant clinically and uniquely suited to being conducted at the CCM. It will be the first to test ghrelin as therapy for sub-acute concussion.

Specific Aims:

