- 1. Describe the change in symptom burden in sub-acute (Part A) and acute (Part B) concussion for the two groups.** This aim defines our primary objective. In Part A we will enroll a maximum of 30 subjects in the open-label treatment Arm (OXE-103) but will stop recruiting when that arm has 20 participants who have completed study requirements. All Part A participants must be diagnosed with a concussion and experience persistent concussion symptoms \leq 28 days post injury. The Part A non-treatment concurrent control Arm will enroll a minimum 20 participants who complete the study requirements, but may continue to recruit more than 20 participants while the Part A open-label treatment Arm is still recruiting. In Part B we will enroll a maximum of 50 subjects but will stop recruiting after each arm (OXE-103 Arm and placebo Arm) has 20 participants who have completed the study requirements. In Part A subjects will receive OXE-103 open-label and in Part B we will randomize 1:1 to placebo versus OXE-103. The Post-Concussion Symptom Score questionnaire (PCSS) will be used as an overall measure of symptom burden. The number of symptoms and severity at each time point are also measures of interest. In addition, subjects will be asked to identify and rank the 4 most bothersome symptoms. We hypothesize that changes in these most bothersome symptoms may have a higher correlation to improvement in quality of life. A visual comparison of change in the two groups will be made. We will consider a change of 20% to be clinically meaningful. Our primary aim will describe the change in symptoms between day 1 and day 15.
- 2. Describe the change in quality of life between the two groups.** This aim defines one of our secondary objectives. To assess this, we will administer the Quality of Life after Brain Injury scale (QOLIBRI) and a Patient Global Assessment of Status (PGAS). A change of 20% will be considered clinically meaningful. Our primary objective with this aim will assess the change between days 1 and 15.
- 3. Describe the correlation between the change in symptom burden and quality of life.** This is an exploratory aim. We hypothesize that improvement in symptom burden will correlate with improvement in quality of life measures. This may be more evident in the correlation between the change in the 4 most bother symptoms and quality of life measures. This aim will describe this correlation between days 1 and 15.

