- AWS complies with the ISO 27018 implementation guidance of controls applicable to public cloud personally identifiable information (PII) protection that supplement the ISO 27002 guidance and the ISO 27001 standard.

Information that will be transmitted from the app is limited to subject code, survey responses, and timestamps of survey responses. No location data will be transmitted. The vendor will not be permitted to attempt to re-identify subjects.

The iPads will be supplied by Oxeia Biopharmaceuticals.

ECG monitoring will be conducted via AliveCor's Kardiastation digital 6 lead ECG. Kardiastation has multiple 510(k) Class II device approvals through the FDA. Kardiostation is a Class II medical device cleared by the FDA for acquiring ECGs in the physician office. Kardiostation uses a HIPPA compliant smartphone app and cloud based database for storage of ECGs. ECG parameters evaluated and captured in the study database will include RR, PR, QRS, and QT intervals as well as normal sinus rhythm. Any clinically significant ECG findings will be recorded as an AE. All ECGs will be kept for the Clinical Trials File.

Statistical Analysis:

This pilot study will describe changes observed within Part A and Part B: placebo versus OXE-103. Since the study is exploratory, analysis will focus on descriptive comparative statistics and not on a prespecified statistically significant primary endpoint. Data will be used to enable power calculations and the definition of suitable clinical endpoints for further clinical development. Data from all Study Days 1, 4, 8, 11, 15, 21, and 44 will be analyzed.

The primary objective will be to determine the proportion of subjects (responders) who experience a clinically meaningful benefit as defined by a reduction of 20% in both the number and severity of concussion related symptoms. Concussion related symptoms will be measured using the 22 symptom PCSS. Severity of each of the 22 symptoms is graded by the patient on a 7-point Likert Scale. This scale has been used extensively to assess patients with concussion/mTBI[18, 19].

In addition, in order to control for the effect of changes in clinically minor symptoms on the overall number and severity of the PCSS, data will also be analyzed based on change of the

4MBS for each subject. This type of analysis has been employed in evaluation of patient reported outcomes for migraine and is discussed in an FDA guidance document (Dodick et al. 2018, Migraine 2018 FDA).

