Outcomes for the investigation of the effect of OXE-103 will be based on self-reported symptom scoring, quality of life questionnaires, computerized cognitive testing assessing executive function, memory and processing speed, and accelerometer-based balance scoring. Safety assessments will include collection of adverse events, clinical laboratory samples, electrocardiograms (ECGs), vital signs including body weights, suicide screening and physical/neurological examination findings.

3. Study Objectives

The primary objective of this study is to describe the change in symptom burden of subacute or acute concussion for the two treatment groups in each part, as measured by the change from baseline to Day 15 in the Post-Concussion Symptom Score questionnaire (PCSS) total score, total number of symptoms and total score for the 4 most bothersome symptoms (4MBS, as identified on Day 1). Improvements of $\geq 20\%$ will be considered clinically meaningful.

The secondary objectives are to:

- Describe the change in quality of life for the two groups in each part as measured by the change from baseline to Day 15 in the Quality of Life after Brain Injury (QOLIBRI) total score and Patient Global Assessment of Status Visual Analog Scale (PGAS VAS).
- Describe changes in cognitive performance for the two groups in each part as measured by the change from baseline to Day 15 in the BrainCheck composite score.

Exploratory objectives of the study are to:

- Describe the correlation between the change in symptom burden and quality of life during the treatment period for each group in each part.
- Describe changes in symptom burden and quality of life at different time points for the two groups in each part.

4. Sample Size

The exploratory nature of this study is such that it is not powered to yield statistically significant outcomes, but will allow detection of trends within subjects and between groups within each part, will support comparison with standard tests of neurocognitive functions, and will provide sample size estimates for future studies of individuals with acute or persistent concussion related symptoms.

The study will enroll a maximum of 50 subjects in each part, but may stop recruiting if each group has at least 20 participants who have completed the study.

5. Outcome Measures

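### Part A's open-label, self-selected, no-treatment contrast does not estimate a drug-versus-placebo effect, yet the plan offers planning data for persistent-symptom trials without saying so

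*Protocol*

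**What the plan says.** **Purpose.** Protocol, Proposed Clinical Trial, says the study "will provide sample size estimates for future studies of people with persistent concussion related symptoms". SAP section 4 words it more broadly: "will provide sample size estimates for future studies of individuals with acute or persistent concussion related symptoms". Protocol, Statistical Analysis, adds: "Data will be used to enable power calculations and the definition of suitable clinical endpoints for further clinical development". None of these sentences names a part, a method or an effect measure.

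**Population.** Protocol, Specific Aim 1: "All Part A participants must be diagnosed with a concussion and experience persistent concussion symptoms", with entry up to 28 days after injury. Part B takes acute patients within 24 hours of presentation to the Trauma Unit.

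**Part A comparison.** Protocol, Proposed Clinical Trial: "In Part A we will compare an open-label treatment arm (OXE-103) to a non-treatment concurrent control arm". The Day 1 flowsheet for Part A sets out how people reach the control arm: "If they decline, they will be offered participation in non-treatment control Arm", and "If subjects choose treatment and fail screening, they may be offered non-treatment control Arm option". SAP section 6.13 plans no modelling and no covariate adjustment.

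**How the comparison is labelled.** Protocol, Statistical Analysis: "This pilot study will describe changes observed within Part A and Part B: placebo versus OXE-103". SAP section 2 describes both parts as randomised, double-blind and placebo-controlled. SAP section 6.1 describes the two groups, separately for each part, as placebo and OXE-103. SAP section 1 says that its outcome measures and analyses prevail where they differ from the protocol.

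**The concern.** Planning information is a declared product of this pilot. For persistent symptoms, only Part A supplies the population, and its contrast has at least three non-drug components:

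- **Expectation and injection.** Arm 1 patients know they receive the drug and are scheduled for 2 × 14 = 28 injections. Arm 2 patients know they receive nothing. PCSS and PGAS are self-rated, and QOLIBRI is a quality-of-life questionnaire.
- **Contact.** The schedules of events give Arm 1 five clinic visits. Arm 2 has three, with Days 8 and 21 allowed to be remote. Arm 1 also has safety monitoring, which Arm 2 does not.
- **Selection.** Controls are people who declined the drug or who failed screening for it.

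Neither document warns that the resulting difference is not a placebo-controlled effect, and the SAP labels it as one. A team relying on that label could carry the difference into a power calculation and count non-drug effects as efficacy.

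**Working it through.** **1. The plan's own figures.** No alpha, power, effect size, standard deviation or response rate is stated, so there is no power figure to reproduce. The combined maximum for Part A Arm 1 and Part B does check: 30 + 50 = 80.

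**2. Assumptions for illustration.** Two-sided alpha 0.05, 80% power, 1:1 allocation and effects in SD units. By the normal approximation,

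n per arm = 2(1.960 + 0.8416)² / δ² = 15.70 / δ².

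**3. Expectation, injection and contact only (selection set to zero).** Let D be the Part A difference and s the share of it that a placebo arm would also show. The drug-versus-placebo effect is D(1 − s), so the required n is 1/(1 − s)² times the planned n. With D = 0.5 assumed, planned n = 15.70 / 0.25 = 62.8, or 63 per arm.

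| s | D(1 − s) | n needed per arm | ratio to 63 | power with 63 |
|---|---|---|---|---|
| 0 | 0.50 | 63 | 1.00 | 80% |
| 10% | 0.45 | 78 | 1.24 | 71% |
| 20% | 0.40 | 99 | 1.57 | 61% |
| 30% | 0.35 | 129 | 2.05 | 50% |
| 50% | 0.25 | 252 | 4.00 | 29% |

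With D = 0.8 the planned n is 25, and 31, 39, 51 and 99 are needed at the same non-zero shares. The ratio depends on s, not on D, apart from rounding.

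**4. Responder scale.** The protocol's primary objective is a responder proportion. Assume 75% response on OXE-103 and 50% untreated. The usual two-proportion formula, with pooled variance under the null, gives 58 per arm.

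| Assumed placebo response | n needed per arm | power with 58 |
|---|---|---|
| 55% | 89 | 62% |
| 60% | 152 | 41% |
| 65% | 329 | 22% |

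**5. Adding selection.** Let the Part A difference be drug effect + expectation effect + b, where b is the bias from self-selected arms. Assume a drug effect of 0.4 (99 per arm needed) and an expectation effect of 0.2.

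| b | Part A difference | planned n per arm | against 99 |
|---|---|---|---|
| +0.2 | 0.8 | 25 | too small |
| 0 | 0.6 | 44 | too small |
| −0.2 | 0.4 | 99 | right |
| −0.3 | 0.3 | 175 | too large |

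The documents do not fix the sign of b. Controls who declined because they were already recovering would make it negative. Controls with a worse prognosis would make it positive.

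**6. Precision.** With 20 completers per arm the standard error of a standardised difference is about √(2/20) = 0.316, and the 95% half-width is 1.96 × 0.316 = 0.62 SD. This applies to Part B as well as Part A, so sampling error alone could mislead planning in either direction.

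**The case against.** The strongest reply has four parts.

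**No sentence says the Part A difference will be the effect size.** The planning statements concern the whole study, and the SAP's version includes acute patients. Planning also needs standard deviations, response rates, attrition and a choice of endpoint, all of which Part A can properly supply. This stands. A reader might infer that the plan commits to taking its effect size from Part A; the documents leave that open and do not state it.

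**A later placebo-controlled trial is not specified.** True, but it is a reasonable inference. A matching placebo is available, the Overview looks ahead to larger Phase II efficacy studies, and Outcomes & Study Tools mentions possible Phase 3 registration trials.

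**The labelling evidence is mixed.** In the protocol's Statistical Analysis sentence, the words after the colon can be read as applying to Part B only. The SAP is dated November 2020 and the protocol March 2021, so the SAP text may simply be out of date. Both points are fair. But the SAP gives its own analyses precedence, so its outdated description of Part A cannot be left standing.

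**The study is exploratory, and any harm falls on a later trial.** No participant or analysis here depends on the point, which limits its weight. It does not remove it, because the plan disclaims significance testing and offers planning data as a product instead.

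**Conclusion.** The point holds in a conditional form. The Part A between-arm difference is not an estimate of the drug-versus-placebo effect, neither document says so, and the SAP describes it as placebo-controlled. Used unadjusted to size a placebo-controlled trial in persistent symptoms, it would tend to give too small a trial if the expectation effect is favourable. The required n is about 1.2, 2 and 4 times the planned n at assumed non-drug shares of 10%, 30% and 50%. Those shares are illustrations; nothing in the documents fixes them.

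Three stronger readings are not supported:

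- **That the later trial would necessarily be undersized.** Selection has unknown sign and no adjustment is planned; step 5 shows planned sizes that are too small, right and too large.
- **That the Part A difference is an upper bound on the drug effect.** For the same reason, it could fall below it.
- **That Part B can simply supply the effect size instead.** Its contrast is randomised and blinded, but it comes from acute patients, with about 20 completers per arm.

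**What to change.** 1. In Protocol, Statistical Analysis, and SAP sections 2, 4 and 6.1, describe Part A as a non-randomised comparison of open-label OXE-103 with no treatment. Confine the placebo label to Part B.
2. In the same places, state that Part A supplies standard deviations, the untreated course, attrition and endpoint choice for planning. State that its between-arm difference is reported descriptively, is confounded by expectation, contact and selection, does not estimate the drug-versus-placebo effect, and is not used unadjusted as the effect size in power calculations.
3. Require that any effect size carried forward to a persistent-symptom trial comes with a stated sensitivity range. Note there that Part B's blinded contrast comes from acute patients with about 20 completers per arm.

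The cost is wording only: no added patients, visits or procedures. The sponsor gives up a direct effect-size claim from Part A, and the planning figure may become less favourable.

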This statistical analysis plan (SAP) provides details on the study design, outcome measures and data analyses planned for the exploratory study of ghrelin (OXE-103) in subacute and acute concussion management that is being conducted at the University of Kansas Health System Center for Concussion Management (CCM). The outcome measures and data analyses specified in this SAP supersede any specified in the study protocol, if differences exist.

Any deviations from this plan will be documented in the clinical study report, and will include timing of changes in relation to unblinding of the study.

Pharmacokinetic, anti-ghrelin antibody and/or biomarker samples may be collected for future use and any data analysis will be the subject of a separate SAP.

2. Study Design

This subacute and acute concussion management study will be conducted as a randomized, single center, double-blind, placebo-controlled, parallel group design in two distinct parts. In Part A, subjects will be recruited from the University of Kansas Health System CCM clinics which include Neurology, Sports Medicine, and Neurosurgery/Physical Medicine and Rehabilitation. Subjects who provide written informed consent and satisfy enrollment criteria at the end of a 7-day screening period will be randomized in a 1:1 manner to either the OXE-103 or placebo treatment groups. In Part B, subjects will be recruited from the emergency department and enrolled within 24 hours of injury. Treatments will be self-administered subcutaneously twice daily during a 14-day treatment period; the OXE-103 group will receive 40 µg/kg with each dose.

For Part A, clinic visits will be conducted at the start of Screening (Day -7), Randomization (Day 1), Day 8, End of Treatment (Day 15), 1 week after the end of treatment (Day 21) and End of Study (Day 44).

Phone contacts will be done during Screening (Day -3) and during treatment (Days 4 and 11). Part B subjects will follow the same schedule except that there will be no screening visit or phone contact.

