6.1 General Methods

This pilot study will describe changes observed in the two treatment groups, placebo versus OXE-103, separately for each part. Since the study is exploratory, analyses will focus on descriptive comparative statistics and not on a pre-specified statistically significant primary endpoint. Data will be used to enable power calculations and the definition of suitable clinical endpoints for further clinical development. Data from baseline and on Study Days 4, 8, 11, 15, 21, and 44 will be analyzed. Note that day definitions in this study will follow the Clinical Data Interchange Standards Consortium in that there is no Day 0;

assessments performed prior to randomization will be done on Days -7 and -3 (Part A only) and randomization is considered Day 1.

For all evaluations of changes from baseline, baseline is defined as the last reported value before the first dose of study drug. In most instances, this will be the value recorded on Day 1.

For the evaluation of safety, a treatment-emergent finding is any result that is newly reported after the first dose of study drug. This may include an existing condition which worsens in severity after the start of treatment.

Continuous variables such as total score or change from baseline will be summarized by the number of observations, mean, standard deviation, median, minimum and maximum value. Graphs of changes from baseline over time will present the means and 95% confidence intervals.

Binary or categorical variables will be summarized by the number of observations in each category along with the percent of observations.

To aid in interpretation of the importance of relationships, correlation coefficients (Pearson and Spearman) will be reported with p-values.

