6.8 Efficacy Analysis

As described previously, binary variables (responders) and continuous variables (values and changes from baseline) will be summarized with appropriate descriptive statistics for each treatment group and each visit (as needed). Changes from baseline over time will also be presented graphically with means (95% confidence intervals) with both treatment groups presented on the same figure.

To evaluate the appropriateness of the current responder definitions, a Receiver Operating Characteristic (ROC) analysis will be performed for each response outcome measure. The current definitions indicate that a ≥20% improvement over baseline is required for a subject to be considered a responder. In the ROC analysis, the percent improvement will be varied from 5% to 95% to determine which percentage is best for distinguishing OXE-103 treated subjects from placebo subjects. If data suggest an early treatment response, the ROC analysis may be performed for a time point earlier than Day 15.

FDA pre-IND guidance from the FDA on the clinical development of OXE-103 advised that “***The outcome measure should be constructed in a way that ensures that a score change is indicative of a meaningful improvement in how a patient feels or functions that comes from a treatment effect specific to mild TBI.***” Pearson and Spearman correlation coefficients (and p-values) will be calculated to examine

relationships between the PCSS changes and changes in the quality of life measures (QOLIBRI total score and PGAS VAS).

Relationships between PCSS changes and changes in cognition and balance (BrainCheck composite measure) will also be examined using correlation coefficients.

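### No OXE-103-minus-control difference with a 95% interval is planned for mean change or responder rate, and responder rates get no interval at all

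*Protocol*

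**What the plan says.** Protocol, Specific Aims, Aim 1 (the primary objective): "A visual comparison of change in the two groups will be made". No statistic is attached to that comparison.

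SAP section 1 gives the SAP precedence: "The outcome measures and data analyses specified in this SAP supersede any specified in the study protocol, if differences exist". Its efficacy plan is as follows.

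- Continuous outcomes (6.1) are "summarized by the number of observations, mean, standard deviation, median, minimum and maximum value". Section 6.8 applies this by treatment group and visit.
- Intervals appear only on graphs of continuous change. In 6.8: "Changes from baseline over time will also be presented graphically with means (95% confidence intervals) with both treatment groups presented on the same figure".
- Responder outcomes (6.1): "Binary or categorical variables will be summarized by the number of observations in each category along with the percent of observations".
- Section 6.13 plans no statistical modelling.
- The one other analysis that sets the arms against each other is the ROC search in 6.8. It varies the responder cut-off from 5% to 95% to find the value that best separates OXE-103 from placebo.

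On purpose, SAP section 4 says the study is not powered, should pick up trends between groups within each part, and "will provide sample size estimates for future studies of individuals with acute or persistent concussion related symptoms". The protocol says much the same under Proposed Clinical Trial.

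**The concern.** The quantity of most interest in a controlled pilot is the contrast with control and how precisely it is known. Change within an arm cannot stand in for it: the protocol's inclusion criteria set a symptom-score threshold because some spontaneous resolution is expected. Yet every planned efficacy table describes one arm at a time, and the ROC search looks for a cut-off and does not yield an effect estimate with an interval.

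The gap is widest for responders. Three of the six primary measures in SAP 5.1 are responder outcomes, and the protocol's Statistical Analysis section makes the responder proportion the primary objective. Those outcomes would be reported without any statement of uncertainty. For continuous outcomes the reader would have two separate intervals on a figure and no stated way of reading them against each other.

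**Working it through.** The plan gives no power or sample-size calculation, so there is no figure of its own to reproduce. The checks below show what the planned output does and does not convey.

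**Inputs.** The target is 20 completers per arm (protocol, Aim 1 and General study design). Assumptions not in the documents: exactly 20 against 20 analysed, equal SDs, normality, two-sided 95% intervals, and the example means, SD and responder counts.

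**1. Two per-arm intervals against one interval on the difference.**

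- Per-arm half-width: t(19) × SD/√20 = 2.093/4.472 = 0.468 SD. Two such intervals stop overlapping when the means differ by more than 2 × 0.468 = 0.936 SD.
- Half-width for the difference: t(38) × SD × √(2/20) = 2.024 × 0.3162 = 0.640 SD.
- Expressed as a t statistic, non-overlap needs 0.936/0.3162 = 2.96 on 38 df, a two-sided p of about 0.005.

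So for observed differences between 0.64 and 0.94 SD, the difference interval excludes zero while the plotted intervals still overlap. By the noncentral t distribution:

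| True difference | Plotted intervals separate | Difference interval excludes 0 |
|---|---|---|
| 0.5 SD | 10% | 34% |
| 0.8 SD | 35% | 69% |

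These rows matter only to a reader who takes overlap to mean no difference.

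**2. Precision in points.** The documents give no SD. For assumed SDs of 10, 15, 20 and 25 points, 0.640 × SD gives half-widths of 6.4, 9.6, 12.8 and 16.0 points.

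**3. Responders.** Newcombe's interval combines the two Wilson intervals (l, u): lower = d − √[(p1 − l1)² + (u2 − p2)²]; upper = d + √[(u1 − p1)² + (p2 − l2)²].

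For an assumed 16/20 against 12/20, the Wilson limits are 0.584 to 0.919 and 0.387 to 0.781.

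- Lower: 0.20 − √(0.216² + 0.181²) = −0.08
- Upper: 0.20 + √(0.119² + 0.213²) = +0.44

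Other assumed counts give:

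| Responders (of 20 each) | Difference | 95% Newcombe interval |
|---|---|---|
| 18 v 14 | +20 points | −5 to +43 |
| 16 v 12 | +20 points | −8 to +44 |
| 14 v 10 | +20 points | −10 to +45 |
| 16 v 10 | +30 points | +1 to +53 |
| 14 v 8 | +30 points | −1 to +54 |

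The plan would show the counts and percentages but not the last two columns.

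**4. Are the sample-size inputs available?** Yes. Take assumed mean changes of −22.5 and −10 with SD 18 and 20 per arm, in the form the SAP tables would give them.

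- Per-arm intervals (±0.468 × 18 = ±8.4): −30.9 to −14.1 and −18.4 to −1.6, which overlap.
- Difference: −12.5 ± 0.640 × 18 = −12.5 ± 11.5, so −24.0 to −1.0.
- Next trial, 80% power, two-sided 5%: 2 × (1.960 + 0.842)² × 18²/12.5² = 32.6, so 33 per arm.

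All of this can be derived from the planned tables, but none of it is planned as output.

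**5. Precision of the SD.** With 38 df the 95% limits are √(38/56.90) = 0.82 and √(38/22.88) = 1.29 times the pooled SD. Squared, a follow-on sample size at a fixed target difference ranges from 0.67 to 1.66 times its point value. This reflects the size of the pilot and would be the same under any analysis. The point is only that it should be shown.

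**The case against.** The study calls itself exploratory, disclaims power, and names no significance endpoint. The SAP refers to comparative descriptive statistics and would place the arms side by side numerically as well as graphically, so comparison by eye is not the whole plan. That is fair, and it justifies leaving out p-values. It does not justify leaving out an estimate and its interval, which are themselves descriptive.

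Two stronger readings are tempting, and the documents do not support them.

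- **That the sample-size inputs will not be produced.** They will be: n, mean, SD and responder percentage by arm are all planned, and step 4 derives a next-trial size from figures of that kind.
- **That real trends will be missed.** That follows only if overlap is read as no difference, and neither document states such a rule.

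Two cautions about the remedy also stand.

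- In Part A, people who decline the drug, or choose it and fail screening, may enter the control arm (protocol, Part A Day 1 flowsheet). An interval there reflects sampling error and leaves selection untouched, so it does not estimate the effect of treatment.
- Six outcomes at six post-baseline visits make 36 intervals per part. Without a lead time point and a clear label, they would invite informal significance reading.

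**Conclusion.** The concern holds in a limited form. Neither document plans a between-arm difference with a 95% interval for mean change or responder rate, and responder outcomes have no interval at all. What is lost is a planned effect estimate and its stated precision; the raw material for later sample sizes is kept.

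The gap between 0.94 SD and 0.64 SD illustrates why the figure is a poor substitute. It depends on an overlap rule that the plan does not contain, and on 20 per arm with equal SDs. Actual numbers may differ, because SAP 6.2 bases efficacy on the per-protocol set and the Part A control arm has no maximum. The responder intervals rest on invented counts; across those tried, a 20-point gap always came with an interval that included zero.

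This is an inexpensive improvement that should be made. It does not invalidate the design.

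**What to change.** In SAP 6.1 and 6.8, for Day 15 in randomised Part B, add:

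1. the OXE-103-minus-placebo difference in mean change, with a 95% interval, for PCSS severity, number of symptoms, 4MBS, QOLIBRI, PGAS and BrainCheck;
2. the difference in responder proportions for the three responder measures, with a 95% Newcombe interval;
3. the pooled SD of each change score with its 95% interval.

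Replace the visual-comparison sentence in protocol Aim 1 with a reference to these estimates. Give the same figures for Part A, labelled as a non-randomised contrast that does not estimate a treatment effect. Treat other visits as supportive, and label all intervals descriptive and unadjusted for multiplicity. If a Part B difference adjusted for the Day 1 value is also reported, amend SAP 6.13, which currently rules out modelling.

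The cost is SAP wording, one protocol sentence and a few table columns. No patients, data, p-values or power claims are added. The SAP (30 November 2020) predates the current protocol (28 March 2021) and still describes Part A as randomised against placebo, so it needs revision anyway.
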